6. STUDY DESIGN

The VRH4L trial is an interventional, randomized, controlled, single-center, parallel group trial. Randomization will be done as a block randomization with a 1:1 allocation^{xix}

Clinique Saint-Jean Brussels (SJ), where the study takes place, is an academic hospital in the center of Brussels with around 2000 deliveries per year.

We create two groups: the VRH group and the control group. During the intervention (T1-3) the VRH-group receives a digital sedation in contrary to the control group who will not use the VRH headset.

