3. SYNOPSIS

STUDY TITLE	A randomized controlled, single centre, study evaluating the impact of Virtual Reality Hypnosis during labor										
SHORT TITLE	VRH4L (Hypnotic Virtual Reality for Labor pain relief)										
PROTOCOL NUMBER	2										
SPONSOR	Department of Anesthesia, Clinique Saint-Jean Bruxelles (SJ)										
STUDY POPULATION	Women during labor										
PHASE	Prospective interventional Randomized Controlled Trial (RCT)										
STUDY DESIGN	
This prospective interventional RCT will evaluate efficacy of Virtual Reality Hypnosis (VRH) in reducing pain during labor. Hypnosis is delivered as a standardized therapeutic intervention through virtual reality, using a digital sedation software. This VRH module is called AQUA[©] (Oncomfort SA) and is specifically designed for the management of pain and anxiety during labor.
 
Women who are planning to give birth at the St-Jean Hospital are recruited at prenatal consultation some weeks before the calculated delivery date. Only patients with a planned induced labor can be included. Patients who agree to participate sign an informed consent form.
 
38 patients will be randomized in two arms (19 patients in each cohort):
 
 Patients in the intervention groups will receive a session of the AQUA[©] Digital Sedation module when in active labor (cervical dilatation ≥ 4 cm, contractions every 5 minutes, NRS pain score $\geq 4/10$) on top of the standard of care Patients in the control group will receive standard of care only. 
Patients are allowed to discontinue the VRH session at any time. A study staff member is present during the session to explain the intervention and fill in the questionnaires. Furthermore, she/he ensures the patient is receiving appropriate clinical care throughout the duration of the intervention.
 
Information from patient's report will be collected before the intervention, after the intervention and up to the patient's discharge from the maternity on day after childbirth. A log will be kept of patients who refuse to participate in the study.
										

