5. STUDY OBJECTIVES

5.1 PRIMARY OUTCOME

The primary endpoint is to compare the differences in NRS pain measured before and after the intervention during labor. (T3 minus T1) The Pain Numerical rating Scale (NRS) is a scale from 0 to 10 well known by the medical staff.^{xv xvi}

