9. SCHEDULE OF ASSESSMENTS AND PROCEDURES

RCT T	TO	T1	T2	T3	T4	T5	T6
Delivery Phase	Prenat consult	Active Labor (study threshold) Day 0	Labor	Labor	Labor	End of Delivery	Day 1
		Before the Start AQUA	During AQUA	End AQUA	T3+30 min		
Screening/ ICF	X						
Refusal questionnaire	X						
Patient Questionnaires & Observation							
NRS pain		X		X	X		
Nausea		X		X	X		
Likert satisfaction							X
CPOT (VR comfort scale)			X				
Willingness to repeat (intervention)							X
Recommend (intervention)							X
Practitioner questionnaire							
Monitored contractions (on the CTG during intervention)				X			
Satisfaction midwife						X	
Quality of the therapeutic relationship						X	
Objective criteria							
Vital signs (Saturation)		X	X	X	X		
Medication received							X
Epidural				X	X		
Progression of labor							X
(Serious) adverse events		X	X	X	X	X	
Stop of digital sedation session				X			

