10. SELECTION AND WITHDRAWAL OF SUBJECTS

During the prenatal visit (PNV = T0; some weeks before the due date) the pregnant women receive information about the the study and the use of VRH from the midwife. Each patient will be asked for participation in the study, after verifying the presence of the inclusion criteria and absence of any exclusion criteria. The registration checklist is filled in (questionnaire 1). If patients refuse, their motivation will be noted on the refusal questionnaire(questionnaire 4). All the included patients receive sufficient information and time to decide if they want to participate or not. After signing the informed consent (Questionnaire 2 resp) they will be immediately randomized using block randomization (with excel). This will assign the pregnant woman to either control group or the VRH group.

On the day of delivery every included patient will receive standard of care. When the women selected in the VR group are in active labor (NRS pain ≥ 4 , cervical dilatation ≥ 4 cm and regular contractions (every five minutes) we present the VRH treatment (T1).

Patients who refuse the VRH treatment (T1) or remove the VRH headset during(T2) will be asked to fill in questionnaire 4 (refusal questionnaire). They will be considered as drop outs.

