11. STATISTICAL CONSIDERATIONS AND ANALYTIC PLAN

11.1 SAMPLE SIZE

The sample size of the study is computed on the basis of expectations for the the difference of the pain NRS means between the two arms at final analysis. Based on previous studies (Yildrim 2004 and Harmon 1990), we may expect a difference of the pain NRS means of 2 or more between the two arms, with a standard deviation of the pain NRS of 2 in both arms. For a statistical power of 80%, an alpha error of 5% and a two-sided test, 17 evaluable patients are needed in each group to reach statistical significance (calculation performed with Stata/MP 14.1).

Assuming a potential drop out rate of 10% in each arm, a total of 19 patients need to be randomized to each arm. The total number of patients for the study is 38.

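### T3, and with it T4, is defined only by the end of the AQUA session, so the control arm has no stated time for the second half of the primary endpoint

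*Combined protocol and SAP*

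**What the plan says.** Section 5.1 sets the endpoint: "The primary endpoint is to compare the differences in NRS pain measured before and after the intervention during labor. (T3 minus T1".

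The schedule in Section 9 gives the T1 column two labels, one clinical, "Active Labor (study threshold) Day 0", and one tied to the device, "Before the Start AQUA". The T3 column says only that the woman is in labor and that AQUA has ended. T4 is 30 minutes after T3, and Section 5.2 likewise counts it from the end of the intervention.

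On the control arm, Section 6 says: "During the intervention (T1-3) the VRH-group receives a digital sedation in contrary to the control group who will not use the VRH headset".

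The active-labor threshold (NRS pain of at least 4, dilatation of at least 4 cm, contractions every five minutes) is spelled out for the VRH arm only. The Synopsis puts it in the bullet on the intervention group. Section 10 introduces it with "When the women selected in the VR group are in active labor".

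On early stopping, the Synopsis says "Patients are allowed to discontinue the VRH session at any time". Section 10 counts women who refuse VRH or take the headset off as drop-outs, whereas Section 11.4 keeps every randomized patient in the ITT analysis. Section 11.3 states that the investigators are not blinded, because they can see who wears the headset while they take measurements.

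**The concern.** A change score needs two measurement times. Controls never start or end AQUA, so the schedule's only rule for T3 cannot be applied to them, and T4 inherits the gap. Half the randomized women have no written time for the second primary measurement.

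Pain may change with time alone during active labor. If controls are rated after a shorter or longer interval than VRH women, or at a different point in labor, that drift is added to the VRH effect or taken away from it. Randomization does not protect against this, because the timing is settled after allocation and by people who know the allocation. A clock time not written down at the bedside may not be recoverable later, so the analysis might be unable to adjust for it.

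**Working it through.** **1. Is there a time rule for each arm?**

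| Time point | VRH arm | Control arm |
|---|---|---|
| T1 | Threshold met (Synopsis, Sections 9 and 10), before AQUA starts | Threshold label in Section 9 only; no operating text |
| T3, session completed | End of AQUA (Section 9) | None stated |
| T3, headset removed early | Not stated | Not applicable |
| T4 | T3 + 30 min | Depends on the missing T3 |
| Minutes from T1 to T3 | Not stated | Not stated |

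No section gives an AQUA running time, or a matched or sham period for controls.

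**2. The plan's own sample size.** Section 11.1 starts from this effect: "we may expect a difference of the pain NRS means of 2 or more between the two arms". Its other inputs are an SD of 2 per arm, 80% power, two-sided 5% alpha and 10% drop-out. For a two-sample t-test the required n is 16.71, rounded up to 17 per arm. At n = 17 the noncentrality is 2 / (2 × √(2/17)) = 2.915 with 32 degrees of freedom, and power is 80.7%. Then 17 / 0.9 = 18.9, so 19 per arm and 38 in total. The stated figure is reproduced and is not in dispute.

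**3. What a timing shift could do (illustration).** Let b be the shift in the between-arm difference caused by unequal intervals:

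b = (pain change per hour) × (difference in T1-T3 interval, in hours).

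The documents give neither input. *Assumed*: pain rises 1 to 2 NRS points per hour, and the intervals differ by 15 to 30 minutes. Then b runs from 1 × 0.25 = 0.25 to 2 × 0.5 = 1.0 points, that is 12.5% to 50% of the 2-point target.

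With 17 per arm and SD 2, noncentrality = (apparent difference) / (2 × √(2/17)):

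| Size of b | Rejection rate, no true effect | Power at true difference 2, shift against VRH | Power at true difference 2, shift favoring VRH |
|---|---|---|---|
| 0 | 5.0% | 80.7% | 80.7% |
| 0.25 | 6.4% | 69.6% | 88.9% |
| 0.5 | 10.9% | 56.4% | 94.2% |
| 1.0 | 29.3% | 29.3% | 98.9% |

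For example, b = 0.5 with no true effect gives noncentrality 0.5 / 0.686 = 0.729 and a rejection rate of 10.9%. The figures apply to a systematic shift in one direction.

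**4. A limit on these figures.** Section 11.1 gives SD 2 for the pain score, not for its change. If both scores have SD 2 and correlation ρ, the change has SD 2 × √(2(1 − ρ)), which equals 2 only when ρ = 0.5. Another correlation would alter every row of the table, but not the gap in the timing rule.

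**The case against.** The strongest reply is that the gap is narrower than it looks. Several things that a reader might infer are not in the documents.

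- *That controls have no T1 at all.* Section 9 also ties T1 to the active-labor threshold, with no restriction to one arm, and staff could apply that to a control. Her T1 is incompletely worded, not absent.
- *That the two intervals do differ.* No section says so. Section 6 treats T1 to T3 as one period during which one group wears the headset and the other does not, and staff might in practice use equal intervals.
- *That T3 moves earlier when the headset comes off.* This is plausible under a rule based on the end of AQUA, but no section says when these women are rated.
- *That investigators are given the choice of when to rate controls.* The plan says only that they are unblinded. The data collection form (Questionnaire 3) is not reproduced and may carry timing instructions.

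The magnitude also rests on assumed values, and its direction is unknown.

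All of this stands as a limit on the claim. It does not supply the missing rule: control T3 and T4 have no time in the text, and neither does T3 after early removal. Nor would a note on a data form replace a definition of the primary endpoint in the protocol.

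**Conclusion.** The point holds in this form: control T3 and T4 are unspecified, control T1 is incompletely specified, and T3 is unclear for women who remove the headset early yet remain in the ITT analysis. The primary change may therefore cover different intervals in the two arms. The documents do not show that it does.

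The size cannot be derived from the documents. The illustrative figures (about 11-29% rejection under no effect for a shift of 0.5 to 1.0 points, or power falling to about 29% for a shift of 1.0 against VRH) depend on an assumed rate of pain change, an assumed interval mismatch, SD 2 for the change and 17 evaluable per arm. They show that a modest timing difference could matter in a trial of this size. They do not predict a bias.

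The timing should still be settled before the first patient is rated. The rule for the primary endpoint cannot be carried out as written in half the patients, and the remedy is cheap.

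**What to change.** The change concerns assessment timing only and touches Sections 5.1, 9 and 10.

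1. State the existing active-labor threshold as the T1 assessment trigger in both arms. Take T1 when the criteria are documented as met: immediately before the headset is started in the VRH arm, and at the same documented point in controls. Documentation is the workable anchor, because Section 5.2 rules out extra cervical examinations and the first moment of 4 cm is not observed directly.
2. Set T3 at one prespecified clock interval after T1 in both arms, equal to the nominal AQUA running time plus a short set-up allowance. The allowance is needed because a late start could otherwise put T3 inside the session, when Section 5.2 says staff cannot communicate with the woman. The sponsor must supply the running time, which the documents do not give.
3. Keep that T3 when the headset is removed early.
4. Keep T4 at T3 + 30 min, and record the actual clock times of T1, T3 and T4 on Questionnaire 3, with headset start and stop times in the VRH arm.

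The cost is wording in three sections and time fields on one form. Treatment and sample size do not change. The small downside is that T3 is no longer the exact moment the headset comes off.

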7. STUDY POPULATION

7.1. INCLUSION CRITERIA

Patients must meet all of the following criteria in order to be eligible for this study:

1. Age: ≥ 18 and ≤ 45 years
2. Pregnant with term gestation
3. Willing to adhere to the rules linked to the use of the VRH headset: turning off mobile phone, visit bathroom in advance, no new visitors and no interference of the partner other than when the woman would ask him so.
4. Provision of written informed consent
5. Induced labor

7.2. EXCLUSION CRITERIA

Patients meeting any ONE of the following criteria are not eligible for this study:

1. Complicated pregnancy (HELLP,...)
2. Scheduled caesarian delivery
3. Receipt of epidural analgesia or opioid painkillers before start active labor phase
4. Low auditory acuity that precludes use of the device
5. Low visual acuity that precludes use of the device
6. Head or face wounds precluding use of the device
7. Schizophrenia
8. Epilepsy
9. Dizziness
10. Non-proficiency in French and/or Dutch (research language)

7.3. INCLUSION CRITERIA FOR INVESTIGATORS

Every investigator will have to obtain the Oncomfort Academy certificate^{xx} and a certificate of Good Clinical Practice (GCP)^{xxi}.

8. CONCOMITTANT MEDICATION AND TREATMENT

The standard labor pain management contains massage, aqua therapy and postural exercises. In our institution, opioid patient controlled intravenous infusion (Remifentanil) or N2O inhalation as analgesia in the first stages of active labor is not standard of care. Every women can ask for and receive (if no contra-indications) an epidural. In this study, however, we will only include patients without an epidural. After childbirth we use paracetamol and anti-inflammatory drugs as first line painkillers. When necessary opioids can be added.

9. SCHEDULE OF ASSESSMENTS AND PROCEDURES

RCT T	TO	T1	T2	T3	T4	T5	T6
Delivery Phase	Prenat consult	Active Labor (study threshold) Day 0	Labor	Labor	Labor	End of Delivery	Day 1
		Before the Start AQUA	During AQUA	End AQUA	T3+30 min		
Screening/ ICF	X						
Refusal questionnaire	X						
Patient Questionnaires & Observation							
NRS pain		X		X	X		
Nausea		X		X	X		
Likert satisfaction							X
CPOT (VR comfort scale)			X				
Willingness to repeat (intervention)							X
Recommend (intervention)							X
Practitioner questionnaire							
Monitored contractions (on the CTG during intervention)				X			
Satisfaction midwife						X	
Quality of the therapeutic relationship						X	
Objective criteria							
Vital signs (Saturation)		X	X	X	X		
Medication received							X
Epidural				X	X		
Progression of labor							X
(Serious) adverse events		X	X	X	X	X	
Stop of digital sedation session				X			

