To compare patient experience in both arms	
Measure of NRS pain after 30 minutes
 
Measure of satisfaction by Likert Scale (0 to 5)
 
Measure of nausea by Nausea and Vomiting Score (0 to 3)
 
Evaluation of comfort during intervention with the CPOT scale (Critical care Patient Observation Tool 0 to 8) and heart rate
 
Willingness to undergo a potential next labor with VRH
 
Willingness to recommend VRH to acquaintances
										
To assess selected safety and efficacy outcomes in both arms	
Progression of labor
 
Need for epidural
										

	
Need for medication: type and dosages during stay
 
Frequency and type of (severe) adverse events (SAEs) (mother and baby)
 
If the patient removes the headset during the session, motivation is documented.

	
To assess gynecologist and nurse satisfaction
 
Measure of satisfaction of the midwife and obstetrician by the Likert scale (0 to 5)
 
Quality of the therapeutic relationship between the midwife and patient (reported by the midwife in a NRS from 0 to 10)

	
Evaluation of vital signs
 
Oxygen saturation
 
Systolic and diastolic blood pressure
 
Heart rate (during and in between contractions)

NUMBERS OF PARTICIPANTS	38
INCLUSION CRITERIA	
 1. Age: ≥ 18 and ≤ 45 years 2. Pregnant with term gestation 3. Willing to adhere to the rules linked to the use of the VRH headset: turning off mobile phone, visit bathroom in advance, no new visitors and no interference of the partner other than when the woman would ask him so 4. Provision of written informed consent 5. Induced labor
EXCLUSION CRITERIA	
 1. Complicated pregnancy (HELLP,...) 2. Scheduled caesarian delivery 3. Receipt of epidural analgesia or opioid painkillers before start active labor phase 4. Low auditory acuity that precludes use of the device 5. Low visual acuity that precludes use of the device 6. Head or face wounds precluding use of the device 7. Schizophrenia 8. Epilepsy 9. Dizziness 10. Non-proficiency in French and/or Dutch (research language)

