5.2 SECONDARY OUTCOMES

30 min after the end of the intervention the NRS pain is assessed once more. (T4)

During the intervention the comfort of the patient is evaluated. (T2) To do this we use the CPOT (Critical care Pain Observation Tool). CPOT is a comfort scale for (non)-ventilated patients in the intensive care unit. We decided to use this score, because during the VR experience we cannot communicate with the patient, which is similar as in sedated patients. And in our own experience we see that the parameters that we look at to evaluate the comfort of the patient during a VR sedation are very similar to this scale. (Facial expression, body movements, muscle tension and vocalization together make a score of 0 to 8)^{xvii} Vital signs like heart rate and blood pressure are parameters that are easily measured during the intervention and considered as objective for evaluating pain during labor. (T1,2,3,4) ^{xviii}

Nausea is also actively evaluated. Therefore we use the PONV rating scale from 0 to 3. (T1, T3, T4) Anxiety is evaluated with the NRS at the same time. (T1, T2, T3) We use the Likert satisfaction scale (from 0 to 5) to explore the satisfaction directly after their experience and the day after delivery. (T3, T6)

Willingness to repeat the intervention and to recommend the intervention can correlate with satisfaction of the overall experience. (T6)

Progression of labor is followed with the degree of the cervix dilatation, therefore we will not perform more cervical examinations than needed but interpret the measurement of the midwives/obstetricians. (T5)

The midwives are asked to evaluate the therapeutic link between themselves and the patient (NRS) after the women return to the maternity ward. (T5)

All the medication received during the stay on the delivery ward, adverse events and interruptions from the intervention is noted. (T3, T5)

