11.4 ANALYSIS

First descriptive analysis will be performed. Qualitative data will be described by frequency and percentage. Quantitative data will be described by mean, standard deviation, median, minimum, and maximum numbers.

Regarding the primary outcome, NRS pain score before and after the intervention will be compared using paired t-test or Mann-Whitney test, depending of data distribution. 95% confidence intervals will be provided.

Regarding secondary outcomes, chi-squared tests will be used to compare frequencies and rates between groups. In case of small cell sizes, we will alternatively use the Fisher's exact test. T-Test or Mann-Whitney test will be used to determine if there is a significant difference between means of the two groups. T-Test or Mann-Whitney test will be also used for all continuous data normally distributed or not such as NRS, Likert scale and physiologic data. Repeated measurements such as Anxiety and Nausea will be handled with appropriate techniques such as paired tests.

Safety variables include the incidence of Serious Adverse Events (SAEs), discomfort and the quality of immediate and distant labor pain analgesia. These data will be tabulated by treatment groups and overall, in contingency table for percentages or in descriptive univariate analyzes for continuous variables.

The Intent-to-Treat (ITT) population will be used for all efficacy and safety analyzes unless otherwise specified. This ITT analysis will include all randomized patients, according to their allocation group.

The Per-Protocol (PP) population will be used to validate the effectiveness of the studied intervention, as specified by the primary outcome. This PP analysis will include all patients in the ITT population who do not have a major violation of the protocol. The list of major violations includes at least:

- Non-administered medication
- Failure to meet an inclusion or exclusion criterion

Patients identified as having major violations will be screened to determine their final exclusion from the PP population, prior to the freezing of the database.

12.QUALITY CONTROL AND QUALITY ASSURANCE

Increased adherence to the protocol is acquired by multiple information sessions about the study for the midwives. Furthermore, a reminder poster will be displayed in their office. Adherence to the protocol by the participants will be monitored daily by a non-blinded investigator (LP) by looking at the daily reports of the study.

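### CPOT comfort is scored only at T2 and compared between arms without adjustment; a T1 baseline in the model would be a cheap gain in precision

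*Combined protocol and SAP*

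**What the plan says.** - **Timing.** In section 9 the row "CPOT (VR comfort scale" is marked at T2 and nowhere else. NRS pain, nausea and vital signs are all marked at T1. Section 5.2 agrees: "During the intervention the comfort of the patient is evaluated. (T2").
- **Reason for the scale.** Section 5.2 says CPOT was chosen "because during the VR experience we cannot communicate with the patient".
- **Status.** The synopsis words the endpoint as "Evaluation of comfort during intervention with the CPOT scale (Critical care Patient Observation Tool 0 to 8) and heart rate". It stands under the objective "To compare patient experience in both arms", so it is a secondary between-arm endpoint.
- **Analysis.** For secondary outcomes section 11.4 states: "T-Test or Mann-Whitney test will be used to determine if there is a significant difference between means of the two groups". It names no covariate-adjusted model for any outcome.
- **Size.** Section 11.1 derives 17 evaluable women per arm, and 19 randomized per arm, from NRS pain. No SD, effect or sample size is given for CPOT.

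**The concern.** CPOT is the only pain or comfort score scheduled during the session, since NRS pain is not taken at T2. Section 10 opens the intervention at NRS pain of 4 or more and dilatation of 4 cm or more, with no upper limit, so women may differ considerably in comfort before the session starts. In an unadjusted comparison of T2 scores, all of that spread stays in the error term.

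What is at stake is precision. If comfort before the session predicts comfort during it, a small trial gives up power that a baseline-adjusted model would recover. A T1 CPOT that was not recorded cannot be reconstructed afterwards.

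**Working it through.** **1. The plan's own figure.** Inputs from section 11.1: difference 2, SD 2 (standardized difference d = 2/2 = 1), two-sided alpha 5%, power 80%. By the noncentral t, power is 78.1% at 16 per arm and 80.7% at 17 per arm, so 17 is reproduced. With 10% dropout, 17/0.9 = 18.9, which rounds up to 19 per arm and 38 in total.

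**2. Precision of the unadjusted T2 comparison.** At n = 17 per arm, the standard error of the difference in means is √(2/17) = 0.343 SD. With t(0.975, 32 df) = 2.037, the 95% CI half-width is 0.70 SD. The difference detectable with 80% power is 0.99 SD. These figures treat CPOT as roughly continuous.

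**3. Effect of adjusting for a T1 CPOT.** Let ρ be the within-arm correlation of T1 and T2 CPOT. The documents do not give it, so a range is shown. Relative to the unadjusted analysis, the variance of the arm difference is multiplied by

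f = (1 − ρ²) × (1 + 1/(2n − 4)), with 2n − 3 = 31 df.

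The second factor, 1 + 1/30 = 1.033, is the small-sample cost of estimating the slope. Power uses noncentrality (d/√f) × √(n/2), with d = 0.8 SD assumed. Unadjusted, this is 0.8 × √8.5 = 2.33 on 32 df.

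| ρ (assumed) | f | Change in SE | Detectable difference (SD), 80% power | Power at 0.8 SD |
|---|---|---|---|---|
| unadjusted | 1 | – | 0.99 | 62% |
| 0 | 1.033 | +1.7% | 1.01 | 60% |
| 0.2 | 0.992 | −0.4% | 0.99 | 62% |
| 0.3 | 0.940 | −3.0% | 0.96 | 64% |
| 0.5 | 0.775 | −12.0% | 0.87 | 73% |
| 0.7 | 0.527 | −27.4% | 0.72 | 88% |

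**4. A covariate already collected.** If T1 NRS pain correlated 0.3 with T2 CPOT (assumed), it would leave 1 − 0.3² = 91% of the variance before the small-sample factor. A T1 CPOT with ρ = 0.5 would leave 75%.

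**5. A simple change score.** T2 minus T1 has variance 2(1 − ρ) times that of T2 alone: 1.4 times at ρ = 0.3, equal at ρ = 0.5, 0.6 times at ρ = 0.7. It loses precision whenever ρ is below 0.5.

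**The case against.** The T2-only choice is reasoned. CPOT stands in for self-report while the woman cannot be questioned; at T1 she can speak and gives an NRS score. The endpoint asks about comfort during the intervention, not change in comfort. Both points stand, and they mean that nothing here is a contradiction or an error. They do not rule out a T1 score: women in the control arm wear no headset and must be scored with CPOT in any case if the arms are to be compared.

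A reader might go further than the documents allow in three ways.

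- *That the T2 comparison is biased, or cannot be interpreted.* It is not biased, because the arms are randomized. With 17 per arm, the chance that they differ by more than 0.5 SD at T1 is about 14% (0.5/0.343 = 1.46, two-sided normal), but the 5% test level already allows for chance imbalance of this kind.
- *That nothing is available to adjust for.* There is no CPOT baseline, but NRS pain is recorded at T1, and so are vital signs. Section 5.2 says "Vital signs like heart rate and blood pressure are parameters that are easily measured during the intervention" and places them at T1 to T4. Heart rate is part of the same comfort endpoint.
- *That one more bedside observation would by itself add precision.* Under the tests written in section 11.4 it would change nothing, because they would not use it. Even with a new model the gain depends on ρ, and a low value is plausible for a coarse 0 to 8 score taken under different conditions.

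**Conclusion.** The point holds as a matter of efficiency. The comfort comparison uses no baseline information, and at about 17 per arm it is imprecise. For an assumed difference of 0.8 SD, adjustment for a T1 CPOT adds about 11 percentage points of power at ρ = 0.5 and about 26 at ρ = 0.7, almost nothing at 0.2, and costs under 2 points at 0. Both the effect size and ρ are assumptions.

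It is a low-cost, optional improvement to one secondary endpoint that has no power calculation. The assumption behind the sample size, "we may expect a difference of the pain NRS means of 2 or more between the two arms", concerns NRS pain, so neither the primary endpoint nor the total of 38 is touched.

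**What to change.** 1. **Section 11.4:** compare T2 CPOT between arms with a linear model containing arm and a T1 baseline, and report the adjusted mean difference with its 95% CI. Keep a Mann-Whitney comparison of T2 CPOT as a check, because the score is bounded at 0 and 8 and may be skewed. Do not analyse a simple T2 minus T1 change score.
2. **Section 9 and section 5.2:** add a T1 mark to the CPOT row, scored in both arms before the headset goes on, and use that score as the baseline.
3. **If T1 CPOT is not added:** name T1 NRS pain as the baseline covariate instead. This needs no new observation.

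The choice of covariate should be fixed before any outcome data are examined. The cost is one short observation at a time when NRS pain and vital signs are already being taken, one field on Questionnaire 3 and a few lines in section 11.4. The statistical downside is the power loss of under 2 points if the correlation is near zero.

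### Adverse events are not scheduled between T5 and discharge, although the endpoint covers mother and baby and a Day 1 contact already exists

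*Combined protocol and SAP*

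**What the plan says.** The synopsis lists as a secondary endpoint "Frequency and type of (severe) adverse events (SAEs) (mother and baby"). It attaches no time window to it.

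Two places give the timing of adverse event recording:

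- Section 9 (schedule): the row "Serious) adverse events" is ticked at T1, T2, T3, T4 and T5. T0 and T6 are empty. T5 is headed "End of Delivery" and T6 is Day 1.
- Section 5.2: "adverse events and interruptions from the intervention is noted. (T3, T5").

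Section 11.4 counts the incidence of serious adverse events among the safety variables and has them tabulated by treatment group and overall. Section 13.1 says that every data form leaves room to report possible harms, and refers to a safety-reports article in an appended study agreement.

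There is a contact after T5. Section 5.2 has patients asked about "satisfaction directly after their experience and the day after delivery. (T3, T6"), and the schedule also places willingness to repeat and recommendation at T6. The synopsis describes collection of patient-reported information "up to the patient's discharge from the maternity on day after childbirth".

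**The concern.** A safety endpoint tabulated by arm needs a defined observation window and the same question asked in both arms. Up to T5 the schedule supplies this. After T5 it supplies nothing, although mother and baby stay in the maternity and the woman is seen again on Day 1.

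Two features of the trial make this worth correcting. Section 4.1 presents measuring side effects as part of the trial's purpose and describes the technique as not previously studied for labor pain. Section 11.3 states that the investigators are not blinded. What is recorded after T5 would then depend on someone choosing to write it down while knowing the allocation. A scheduled question reduces the room for such reporting to differ between arms.

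**Working it through.** The check is a comparison of texts. The plan gives no figure on this point to reproduce.

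1. **The schedule row, column by column (Section 9).** T0 blank; T1, T2, T3, T4 and T5 ticked; T6 blank. Of the six on-study time points (T1 to T6), 5 of 6 are covered, and the one left out is Day 1.

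2. **Could the blank be a table-reading artefact?** This is unlikely. Other rows of the same table (satisfaction, willingness to repeat, recommendation) carry their mark at T6, so that column is readable. Section 5.2, which is running text, also ends adverse events at T5. Neither source names T6.

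3. **Where T5 falls.** The column heading is "End of Delivery". Section 5.2, however, has the midwife rate the therapeutic relationship "after the women return to the maternity ward. (T5"). Taken together, T5 lies around the transfer to the maternity ward. Events at birth and on the delivery ward are inside the scheduled window. The uncovered period runs from T5 to discharge, and its length is not stated.

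4. **What could still catch an event in that period.** Section 13.1 allows harms to be reported on any form, and Section 14.2 has forms collected on the first working day after delivery. An event after T5 can therefore reach the database. Section 13.1 itself sets no window and no Day 1 question, and does not mention the baby.

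5. **Agreement between Sections 5.2 and 9.** They differ on this and neighbouring items:

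| Item | Section 5.2 | Section 9 |
|---|---|---|
| Adverse events | T3, T5 | T1 to T5 |
| Medication received | T3, T5 | T6 |
| Progression of labor | T5 | T6 |

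6. **Size of the loss.** The expected number of events in the gap would be the number of women (38), or of mothers and babies, times the probability of an event between T5 and discharge. The documents give no such probability and no duration from which to build one, so no number can be computed.

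7. **Effect on the rest of the design.** The sample size rests on pain scores only: difference 2, SD 2, 80% power, two-sided 5%. The two-sample t-test gives 16.71, so 17 per arm; 17 / 0.90 = 18.9, so 19 per arm; 2 × 19 = 38. The plan's figures reproduce, and adverse event timing is not an input to them.

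**The case against.** The case for leaving the plan alone has several parts.

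- **A chosen window.** Sections 5.2 and 9 both stop at T5, which looks deliberate. Collection before, during, at the end of and 30 minutes after the session, and again at T5, covers the exposure to a non-invasive Class I device. This is a fair argument for a short window. The synopsis endpoint, however, includes the baby and states no such limit. If T5 is the intended end, the endpoint should say so.
- **A contradiction with the synopsis?** A reader might infer that the synopsis promises adverse event collection to discharge and that the schedule breaks that promise. The text does not go so far. The sentence ending "discharge from the maternity on day after childbirth" concerns patient-reported information, which T6 does hold.
- **Is neonatal follow-up essentially zero, with a window that ends at birth?** A reader might infer this from the T5 column heading alone. Section 5.2 ties a T5 rating to the return to the maternity ward, so the inference is not supported.
- **Are Day 1 events missed?** This too is stronger than the documents allow, given Sections 13.1 and 14.2. They are not systematically collected, which is a lesser fault.
- **Unseen material.** Neither Questionnaire 3 nor the safety-reports article is in the supplied text, and Section 12 says that the forms are the same for every patient. The form may already prompt for adverse events in mother and baby. That counts against asserting differential collection, but it does not fill the blank at T6 in the schedule that staff are to follow.
- **Small consequence.** Safety data are only tabulated, and the plan announces no conclusion that the intervention is safe. This stands, and it keeps the point modest.

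**Conclusion.** The point holds in a limited form. Adverse events are scheduled only up to T5, so between T5 and discharge they are not systematically collected, although the endpoint covers mother and baby and incidence is tabulated by arm. Anything recorded in that interval rests on the general reporting option in Section 13.1, used by staff who are not blinded.

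The gap is one of six on-study time points. Its duration and the number of events at stake are unknown. The conclusion assumes that the schedule and Section 5.2 are what staff follow, and that the form and agreement not supplied add no scheduled Day 1 question. If they do, what remains is to bring Sections 5.2 and 9 into line with them.

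The primary outcome, sample size, power and alpha are unaffected. This is an inexpensive improvement to the completeness of the safety comparison, not a fault that undermines the trial.

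**What to change.** - In Section 9, tick (serious) adverse events at T6.
- At that contact, ask about mother and baby separately, with the same wording in both arms, on the existing data collection form. First check whether Questionnaire 3 already has these lines.
- In Section 5.2, state one collection window, T1 to discharge, for both arms.
- In the same edit, reconcile the adverse event timing in Section 5.2 (T3, T5) with Section 9 (T1 to T5), together with the other items in the table above.

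The cost is a few extra form items at a contact that already takes place. No additional visit or participant is needed.
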